each recruitment day, the RAs will use the CERNER list and EMR to review patients' race, age, and previous colonoscopy history. RAs will alert healthcare providers (e.g., physicians and patient navigators) daily of patients who may be eligible for a screening colonoscopy referral. If a patient is eligible for the study (e.g., self-identifies as black/African American, age-eligible for CRC screening, and received a referral for a screening colonoscopy), the physician or patient navigator will briefly introduce the study to the patients at the end of the primary care or GI appointment. Patients who are interested in participating in the study will meet with an RA in a private exam room immediately following their appointment to review and complete the consent form.

If the patient is interested in participating in the study, but unable to complete the study after the clinic visit (e.g., time constraints, first contact with patient navigator is over the telephone, RA is not on site), the patient can provide the healthcare professional (physician or patient navigator) with permission to be contacted by the study research team. The healthcare provider (patient navigator or physician) will then give the research staff the patient's preferred contact information. The research coordinator will then contact the potential participant and schedule a date/time to complete the consent form.

Consented participants will complete a verbally administered baseline questionnaire. Participants will then be assigned to one of two groups: e-Motivate (N=100) or control group (N=100). Participants assigned to e-Motivate condition will receive usual care and will also complete the 20 minute e-Motivate app. Immediately after completing the e-Motivate app, the RA will verbally administer a post-intervention questionnaire that assesses the hypothesized mediators. Participants in the control group will receive usual care (e.g., patient navigation, print materials). Participants will receive \$20 gift card to Target as compensation. Six months following the initial referral, medical charts will be reviewed to determine whether the colonoscopy was completed, the quality of the bowel prep, and process variables (e.g., number of cancellations/rescheduled appointments/no-shows)

g) Specimen Banking

N/A

h) Data Management and Confidentiality

Survey Data:

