Missing data: The e-Motivate is a one-time intervention and thus we anticipate minimal missing data. *Analyses of covariates:* Participants will be randomly assigned to treatment condition and therefore significant baseline differences are not expected. However, contingency tables and t-tests will be performed to determine any differences between the two groups. Using a p value of ≤ 0.15 , any consistent pattern of correlation for any of the covariates would suggest their inclusion in the primary data analysis model.

Analysis of Primary Outcome: The primary outcome (screening uptake) will be assessed with a logistic regression model. The hypothesized moderators will be evaluated individually. The final logistic model will contain the main effect for the treatment group, any identified covariates, and any significant moderators.

Analysis of Secondary Outcome: If bowel prep quality is normally distributed, a t-test will be used to compare the two treatment groups.

Exploration of Mediation: In the mediation analyses, we will first show that treatment predicts the primary outcome. We will next evaluate the extent to which the treatment affects the mediators using a linear mixed model with repeated measures. Time will be entered into the model first followed by any covariates. Next, the binary treatment vector will be introduced as a main effect followed by interaction with time. Since there are three

 Mount Sinai	Protocol Name:	Internet-based Motivational Interviewing for Colonoscopy in African Americans
	Principal Investigator:	[name]
	Primary Contact Name/Contact Info:	[name], [contact] ,
	Date Revised:	8/16/19
	Study Number:	GCO# 14-0275 IF# HS#

correlated mediators, the p-values will be adjusted using the Sidak correction for multiple comparisons. Only the mediators that are predicted by the treatment main effect or the time by treatment interaction will be retained. Each mediator will then be introduced into the logistic model predicting the primary outcome. To establish mediation, the indirect paths from treatment to mediators and from mediators to outcomes will be assessed using 1000 bootstrap samples following the procedures.

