Analysis of Power: We are proposing a sample of 200 participants (100 in each treatment arm) and setting alpha equal to 0.05. In our pilot study, the MI condition was associated with 71.4% (20/28) screening uptake compared to 52.0% (13/25) for the control condition. Based on these results, we are hypothesizing that approximately 71.4% of participants in e-Motivate condition will complete the colonoscopy, compared to approximately 52% of the participants in the control condition. Based on these projections, power is equal to 0.83. Of note, for the proposed study, the control condition will be a print brochure. Previous research suggests that a print brochure produces comparable CRC screening rates (52.0%-53.5%) to our pilot study's attention control condition (52.0%).

i) Provisions to Monitor the Data to Ensure the Safety of Subjects

Part I: Elements of a Data and Safety Monitoring Plan

1. List the name(s) of the individual(s) at the Mount Sinai School of Medicine (MSSM) who will be responsible for data and safety monitoring of this study. For each individual, indicate their role, name, title, and department information.

MSSM Principal Monitor:

Check One: PI: Team Member: Independent:

Last Name: [name]

First Name: [name]

Academic Title: Instructor

Department: Oncological Sciences

Mailing Address: [name]

[contact]

[contact]

E-mail: [contact]

MSSM Additional Monitor:

Check One: PI: Team Member: Independent:

Last Name: [name]

First Name: [name]

Academic Title: Professor

Department: Oncological Sciences

Mailing Address: [name]

[contact]

 Mount Sinai	Protocol Name:	Internet-based Motivational Interviewing for Colonoscopy in African Americans
	Principal Investigator:	[name]
	Primary Contact Name/Contact Info:	[name], [contact] ,
	Date Revised:	8/16/19
	Study Number:	GCO# 14-0275 IF# HS#

[contact]
E-mail: [contact]

2. Justify your choice of principal monitor in terms of the assessed risk to the research subject's health and wellbeing. In high risk studies when the principal monitor is independent of the study staff, indicate the individual's credentials, relationship to the PI, and the rationale for selection.

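### The Aim 2b mediator screen pairs a diluted main-effect test with a change-score interaction; one baseline-adjusted test per mediator has more power at half the false-retention rate

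*Combined protocol and SAP*

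**What the plan says.** The model is in section 5(h) of the combined protocol and SAP, under Data Analyses, Exploration of Mediation: "We will next evaluate the extent to which the treatment affects the mediators using a linear mixed model with repeated measures". The order of entry is given: "Time will be entered into the model first followed by any covariates". Then: "Next, the binary treatment vector will be introduced as a main effect followed by interaction with time". On multiplicity, the plan notes that there are three "correlated mediators, the p-values will be adjusted using the Sidak correction for multiple comparisons". The retention rule is: "Only the mediators that are predicted by the treatment main effect or the time by treatment interaction will be retained". Retained mediators go on to the logistic model for the primary outcome and to the bootstrap of the indirect paths.

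Measurement is described in section 5(f), RCT Procedures. Before assignment: "Consented participants will complete a verbally administered baseline questionnaire". After it, in the description of the app arm: "Immediately after completing the e-Motivate app, the RA will verbally administer a post-intervention questionnaire that assesses the hypothesized mediators". No later mediator questionnaire is described. The control arm's description mentions usual care but no post questionnaire.

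The baseline mediator score is not named as a covariate, and the arms are not constrained to a common baseline mean. The only covariate rule is a screen at p ≤ 0.15, written for the primary model.

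**The concern.** With one questionnaire before assignment and one after, time has two levels, and the score taken before randomisation is modelled as an outcome. The app cannot have affected that score. A treatment main effect that pools the two occasions therefore mixes a post-app difference with a pre-app difference that can only be chance. Yet significance on that term alone is enough to retain a mediator. The other route, the interaction, compares changes between arms, which makes less use of the baseline than regression on it does.

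This step is a gate. A mediator dropped here never reaches the mediation analysis, and one kept because of a baseline imbalance does. What is at stake is how well exploratory Aim 2b can identify the mediators that the app moves.

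**Working it through.** **Inputs from the documents.** Section 5(h), Analysis of Power: "We are proposing a sample of 200 participants (100 in each treatment arm) and setting alpha equal to 0.05". Three mediators with a Sidak correction: per-test level 1 − 0.95^(1/3) = 0.01695, two-sided critical value z = 2.388.

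**Assumptions, not in the documents.** Two-sided tests; the Sidak level applied across the three mediators to each of the two tests; pre and post scores complete in both arms with equal SD; effect δ on the post score of 0.4 SD; pre-post correlation r from 0.5 to 0.7, with values outside that range shown further down.

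**The plan's own figure.** The only power stated is 0.83, for the primary outcome (71.4% against 52%, 100 per arm). A two-sided normal approximation gives 0.81 with pooled variance and 0.82 with unpooled variance, so it is close to reproduced. No figure is given for the mediator model.

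**What each term estimates.** Let B be the observed baseline difference between arms and P the post difference.
- Main effect before the interaction enters: (B + P)/2, with expectation δ/2.
- Interaction: P − B, with expectation δ.
- Main effect once the interaction is in the model, with time coded 0/1 and baseline as reference: B alone.

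A fitted example on simulated data shows this. With B = 0.220 and P = 0.454, the main effect was (0.220 + 0.454)/2 = 0.337 before the interaction entered and 0.220 after. The interaction was 0.234.

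**Variances.** In units of 2·SD²/n: interaction 2(1 − r); averaged main effect (1 + r)/2; baseline-adjusted 1 − r². The ratio of baseline-adjusted to interaction is (1 + r)/2, which is below 1 for every r < 1.

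**Power.** Φ(expected value/SE − 2.388), with SE = √(0.02 × factor) in SD units. At r = 0.5:
- Interaction: SE = √(0.02 × 1) = 0.141; 0.4/0.1414 − 2.388 = 0.44; power 0.670.
- Main effect: SE = √(0.02 × 0.75) = 0.122; 0.2/0.1225 − 2.388 = −0.76; power 0.225.
- Baseline-adjusted: the same SE of 0.122; 0.4/0.1225 − 2.388 = 0.88; power 0.810.

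**The either/or rule.** With equal SDs, the covariance of (pre + post) with (post − pre) is Var(post) − Var(pre) = 0, so the two tests are nearly independent. Power is 1 − (1 − interaction)(1 − main effect).

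| r | Interaction | Main effect | Either/or rule | One baseline-adjusted test |
|---|---|---|---|---|
| 0.5 | 0.670 | 0.225 | 1 − 0.330 × 0.775 = 0.744 | 0.810 |
| 0.6 | 0.781 | 0.210 | 1 − 0.219 × 0.790 = 0.827 | 0.874 |
| 0.7 | 0.897 | 0.197 | 1 − 0.103 × 0.803 = 0.917 | 0.942 |

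False retention per mediator under the either/or rule is 1 − (1 − 0.01695)² = 0.034, against 0.017 for one test. If the single test were also run at 0.034, its power would be 0.873, 0.921 and 0.967.

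**Sensitivity (either/or against baseline-adjusted).** δ = 0.4: 0.632 against 0.718 at r = 0.3, and 0.985 against 0.990 at r = 0.8. At r = 0.5: 0.469 against 0.525 for δ = 0.3, and 0.920 against 0.955 for δ = 0.5.

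**Simulation check (3,000 trials per setting).** With δ = 0.4 and r = 0.5, power was 0.676 for the interaction, 0.743 for the either/or rule and 0.816 for the baseline-adjusted test. With no effect, each single test rejected at 0.014 to 0.020, and the either/or rule at 0.030 to 0.035.

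**The case against.** Several stronger readings are tempting, and the documents do not support them.

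- **The full gap between the interaction and the adjusted test is lost** (0.67 against 0.81 at r = 0.5). It is not. The plan retains on either test, so the either/or rule is the right comparator, and it recovers about half of that gap. It does so by doubling false retention, and it still falls short.
- **The main effect says nothing about the app.** That holds only with the interaction in the model and baseline as the reference occasion. With post as reference, the coefficient is the post difference. The plan gives no coding, and its order of entry suggests that the main effect is tested first, where it is the average.
- **The wrong quantity enters the indirect effect.** The plan uses this model to select mediators and does not say which treatment-to-mediator coefficient is bootstrapped. That is unspecified, not shown to be wrong.
- **The mediator results are biased.** Under randomisation the baseline difference averages zero, the interaction is unbiased, and each single test keeps its size.
- **Controls are not measured after baseline.** Section 5(f) describes the post questionnaire only for the app arm, but a treatment-by-time model implies scores on both occasions in both arms. Baseline measurement of the mediators is likewise implied rather than stated. The power comparison depends on both.

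It is also fair to say that change scores and baseline adjustment are both valid methods, and that the aim is exploratory. What remains is that one test per mediator is better on both error rates and uses scores that the planned model already needs.

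**Conclusion.** The point holds as a matter of efficiency and of a poorly targeted screening test. At an assumed 0.4 SD effect, the planned rule gives up about 7, 5 and 2.5 percentage points of power at correlations of 0.5, 0.6 and 0.7, while admitting null mediators about twice as often as a single test would. The ranking of interaction against adjusted test holds for any correlation below 1. The size rests on the assumed effect and correlation, and the power difference is negligible from about 0.8 upward, although the main-effect term remains diluted at any correlation.

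All of this is conditional on pre and post scores in both arms. Without control post scores, neither the interaction nor the adjusted comparison can be estimated. The primary analysis and its stated power of 0.83 are not affected. Low priority.

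**What to change.** First, state in section 5(f) that the mediators are scored at baseline and again after assignment in both arms, and when the control arm's second questionnaire is given.

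Then, in Exploration of Mediation, replace the main-effect and interaction tests with one test per mediator: the post score regressed on treatment and baseline score. A mixed model with arm means constrained equal at baseline serves the same purpose. Test the treatment coefficient at the Sidak level for three mediators, and name it as the treatment-to-mediator path in the bootstrap.

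If both arms already have both scores, the cost is a few sentences of SAP wording and a simpler model on the same data. If controls have no second questionnaire, one must be added, but the planned interaction needs it too. By the timeline in section 5(d), enrolment would be near its end at the document's date, so scores not taken from controls already enrolled could not be recovered by rewording.

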Primary objective: To conduct an RCT that examines the efficacy of e-Motivate versus a control condition for increasing screening colonoscopy uptake in Black/African Americans. Black/African American patients referred for a screening colonoscopy will be recruited to the RCT. Participants (N=200) will be randomly assigned to an e-Motivate group (N=100) or a control group (N=100). Participants in e-Motivate group will receive usual care and will also complete a one-time, 20-minute e-Motivate app on a tablet immediately following the primary care appointment in which they received a referral for a screening colonoscopy. Participants in the control group will receive usual care (e.g., print handout, patient navigation). It is hypothesized that participants in e-Motivate condition will be more likely to complete the recommended screening colonoscopy.

 Mount Sinai	Protocol Name:	Internet-based Motivational Interviewing for Colonoscopy in African Americans
	Principal Investigator:	[name]
	Primary Contact Name/Contact Info:	[name], [contact] ,
	Date Revised:	8/16/19
	Study Number:	GCO# 14-0275 IF# HS#

Exploratory Aim 2a. To explore the efficacy of e-Motivate for improving a secondary adherence outcome (e.g., bowel prep quality).

Exploratory Aim 2b. To explore mediators and moderators of e-Motivate. As a part of the RCT, potential mediators (i.e., competence, autonomy, relatedness) and moderators (i.e., demographics, Internet fluency/use) will be explored.

2) Background

Colorectal cancer (CRC), a largely preventable disease, remains the second cause of cancer death in the United States in men and women combined. Compared to other racial groups, Black/African Americans have the highest CRC morbidity and mortality rates. Given these disparities, it is critical to increase Black/African Americans' participation in CRC prevention efforts.

A motivational interviewing (MI) intervention can help improve Black/African Americans' screening colonoscopy uptake. MI is a brief patient-centered intervention that increases perceived competence, autonomy, and relatedness in order to promote behavioral change. Extensive research supports the efficacy of MI to promote preventive health screening uptake (e.g., increase HIV testing) and MI has proven efficacious with Black/African Americans across a wide range of diseases. There is strong support for the use of MI to improve Black/African Americans' screening colonoscopy uptake.

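### In exploratory Aim 2b the mediator-to-uptake model neither names the mediator score nor fixes its baseline value as a term, so the indirect effect can be biased in either direction

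*Combined protocol and SAP*

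**What the plan says.** Section 1, Exploratory Aim 2b, states that "potential mediators (i.e., competence, autonomy, relatedness) and moderators (i.e., demographics, Internet fluency/use) will be explored". The analysis is in Section 5(h), Data Analyses, under Exploration of Mediation, and has four steps.

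- Treatment must first be shown to predict uptake.
- The plan then evaluates how far "the treatment affects the mediators using a linear mixed model with repeated measures", with Sidak-adjusted p-values for the three mediators. "Only the mediators that are predicted by the treatment main effect or the time by treatment interaction will be retained".
- The third step turns to uptake: "Each mediator will then be introduced into the logistic model predicting the primary outcome". The terms of that model come from the primary analysis: "The final logistic model will contain the main effect for the treatment group, any identified covariates, and any significant moderators".
- Finally, "the indirect paths from treatment to mediators and from mediators to outcomes will be assessed using 1000 bootstrap samples".

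The baseline mediator score is not named in the logistic model, and the form of the mediator score is not given. The only route by which a baseline score could enter is the covariate rule at p ≤ 0.15. That rule follows a sentence on contingency tables and t-tests between the groups, and it speaks of a pattern of correlation without saying with what.

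On measurement, Section 5(f), RCT Procedures, says "Consented participants will complete a verbally administered baseline questionnaire" before assignment, without listing its contents. It then says "Immediately after completing the e-Motivate app, the RA will verbally administer a post-intervention questionnaire that assesses the hypothesized mediators". No second questionnaire is described for the control group. Section 5(e) mentions a mediator questionnaire for participants but gives no timing.

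**The concern.** Treatment is randomised; the level of competence, autonomy or relatedness is not. A participant who arrives confident will tend to score high afterwards and may be more likely to have the colonoscopy anyway. Without that participant's baseline score in the uptake model, the mediator coefficient mixes the effect of any change the app produced with differences that existed before it. The bootstrap puts an interval round the biased product and does not remove the bias.

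At stake is the mechanism claim. The protocol presents these three constructs as the way motivational interviewing works. Aim 2b could credit a construct whose change did nothing for uptake or, with a change score, hide one that did.

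**Working it through.** **The plan's own figure.** The plan gives no figure for mediation. Its power of 0.83 (100 per arm, 71.4% v 52%, alpha 0.05) is reproduced closely. Unpooled SE = √(0.714×0.286/100 + 0.52×0.48/100) = 0.0674; 0.194/0.0674 − 1.96 = 0.92; power = 0.82. The pooled and arcsine forms give 0.81. This figure matters here only because treatment must predict uptake before mediation is examined, which happens in about 80% of trials.

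**Inputs from the plan.** 100 per arm; uptake 52% and 71.4%; Sidak level for three mediators 1 − 0.95^(1/3) = 0.01695; 1000 bootstrap samples.

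**Assumed inputs, not in the documents.** App shift a = 0.4–0.5 SD, baseline–post correlation ρ = 0.5–0.7, log odds ratio for uptake g = 0.3–0.5 per SD of baseline score, two-sided tests, and post scores in both arms.

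**Null model.** Baseline score M0 ~ N(0,1). Post score M1 = ρM0 + a·treatment + error, with within-arm SD 1. Logit uptake depends on treatment and g·M0 only, so the mediator has no effect.

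**Direction of the bias (approximate, linear scale).**

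- Post score, no baseline term: within arm the slope of M0 on M1 is ρ, so the mediator coefficient is about ρg and the false indirect effect about aρg. Examples: 0.4×0.6×0.3 = 0.07 and 0.4×0.7×0.5 = 0.14 log-odds.
- Change score, no baseline term: Cov(M0, M1−M0) = ρ − 1 and Var(M1−M0) = 2(1−ρ), so the slope is −1/2 and the coefficient about −g/2, that is −0.15 to −0.25. Simulated means were also −0.15 to −0.25.
- Baseline term included: bM1 + cM0 = b(M1−M0) + (b+c)M0. Post and change scores then give the same mediator coefficient, and its true value here is 0.

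**Simulation, post score, a = 0.5, 1000 trials per setting.** Mediation is declared when treatment predicts uptake, the time-by-treatment contrast passes the Sidak level, and the mediator coefficient is significant at 0.05.

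| ρ | g | exp(ρg) | mean OR, no baseline | mean OR, with baseline | declared, no baseline | declared, with baseline |
|---|---|---|---|---|---|---|
| 0.5 | 0.3 | 1.16 | 1.18 | 1.01 | 11% | 2% |
| 0.5 | 0.5 | 1.28 | 1.29 | 1.01 | 24% | 4% |
| 0.7 | 0.3 | 1.23 | 1.24 | 1.02 | 20% | 4% |
| 0.7 | 0.5 | 1.42 | 1.44 | 1.03 | 48% | 4% |

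The simulation standard error is at most √(0.476×0.524/1000) = 1.6 points. A set of settings mixing shifts of 0.4 and 0.5 SD gave 12%–41% without the baseline score and about 3% with it. A 1000-sample percentile bootstrap of the product, without the preliminary tests, gave 30% v 4% at a = ρ = g = 0.5 (200 trials).

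**Effect of the p ≤ 0.15 rule (Sidak step applied, treatment-predicts-uptake step not).**

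- Read as a between-arm test, it admits a randomised baseline score in about 15% of trials. False mediation falls only from 16%–60% to 14%–52%.
- Read as correlation with uptake, with the baseline score a candidate, it admits the score in 96% of trials at g = 0.5 and 68% at g = 0.3. False mediation is 3.3%–4.5%, against 3.4%–4.5% with forced adjustment.

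**Other cases.** With a change score and no baseline term, false negative coefficients occurred in 9%–31% of trials, and false positive ones in well under 1%. With a = 0 and the unadjusted post score, false mediation was at most about 2% (4% in the bootstrap).

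**The case against.** The best defence is that the plan leaves baseline adjustment open and does not exclude it. The covariate rule may mean correlation with uptake, and then it admits the baseline score in most of the trials where it matters. The plan does not list its candidate covariates, so the score is neither in nor out. This stands as a limit on size: under that reading there is almost no excess. It does not settle the matter, because the sentence follows between-group tests and is more naturally read that way.

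A reader might infer that the plan's error rate is one half or more, since rates that high appear when the preliminary tests are left out or stronger associations are assumed. The documents do not support that. They require treatment to predict uptake and a Sidak-adjusted retention step, they do not say that the raw post score is used, and they give none of the assumed correlations.

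A reader might also infer that the bias disappears only if baseline score does not predict uptake. That is wrong: the false indirect effect also disappears if the app does not move the score and, for the post score, if baseline and post scores are uncorrelated.

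Two further points stand. The bootstrap sentence refers to procedures whose source is not visible, so the point concerns the text as available. And the analysis is labelled exploratory.

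**Conclusion.** The gap is real and worth closing, but modest in standing. The mediator-to-uptake model leaves both the score and the baseline term undefined. Under the assumed inputs, with the plan's preliminary tests applied and no true mediator effect, an unadjusted post score yields false mediation in about 12%–41% of trials (11% and 48% at the corners of the table), against about 3% with the baseline score. The size depends on the assumptions and on the less favourable reading of the covariate rule; the direction follows once the app moves the score and baseline predicts both post score and uptake. An unadjusted change score errs the other way. All of this presumes mediator scores at both times in both arms, which Section 5(f) does not establish. Baseline adjustment removes this one confounder; other mediator–uptake confounding remains.

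**What to change.** In Section 5(h), Exploration of Mediation:

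- Name the post-intervention score as the mediator in the uptake model.
- Always include the same mediator's baseline score, with treatment and the primary model's covariates, whatever the p ≤ 0.15 rule shows.
- State that both path models are refitted in each of the 1000 bootstrap samples.

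In Section 5(f), the sponsor should confirm that the mediators are measured at baseline and again after the intervention period in both arms, since the repeated-measures model needs this. If they are, the cost is a sentence or two and one extra parameter per mediator, with no new data. If control participants have no second measurement, neither the planned mixed model nor this correction can be fitted as described, and that must be resolved first. Any report of Aim 2b should say that unmeasured mediator–uptake confounding remains possible.
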